#### Participant Classification for ADA Against Efgartigimod

Table E below gives an overview of how the ADA participant classification will be derived, starting from the participant baseline ADA sample status.

Document: BIOSdata\argenx\Efgartigimod\HAB40220\Biostatistics\Documentation\SAP

Author: Version Number: 1.0

Version Date: 03 June 2024

Template No.: CS\_TP\_BS016 Revision 7 Reference: CS\_WI\_BS005

Page 44 of 54

#### Table E Participant Classification for ADA Against Efgartigimod

	Highest a postbaseline sample status				
Participant ADA classification	ADA negative	ADA positive (missing titer b )	ADA positive (negative titer c or numerical titer value)		ADA unevaluable
Baseline ADA sample status					
ADA negative	ADA negative	Treatment- induced ADA	Treatment-indu	iced ADA	ADA unevaluable
ADA positive (missing titer b )	Treatment- unaffected ADA	ADA unevaluable	ADA unevalual	ble	ADA unevaluable
ADA positive (negative titer c or numerical titer value)	Treatment- unaffected ADA	ADA unevaluable	Titer <4x baseline titer: Treatment- unaffected ADA	Titer ≥4x baseline titer: Treatment- boosted ADA	ADA unevaluable
ADA unevaluable	ADA unevaluable	ADA unevaluable	ADA unevaluable		ADA unevaluable

Error! Reference source not found. Highest sample status, with order (from low to high): ADA unevaluable, ADA negative, ADA positive ("positive immuno-depletion" or "positive titer"), ADA positive with titer <1 ("negative titer"), ADA positive with titer ≥1 (numerical value selecting the sample with highest titer). Error! Reference source not found. Samples with missing titer will have a reported ADA result of "positive" immuno-depletion" or "positive titer".

Error! Reference source not found. Results reported as "negative titer", ie, titer value <1 will be set to a value of 1.

The following definitions will be used in the summary tables:

- ADA evaluable participant = participant classified in any of following categories: ADA negative, treatment-unaffected ADA, treatment-induced ADA, or treatment-boosted ADA. The first 2 categories are classified as "ADA negative", and the latter 2 are classified as "ADA positive";
- ADA incidence = percentage of participants with treatment-induced or treatment-boosted ADA (denominator: number of evaluable participants);
- ADA prevalence = percentage of participants with treatment-unaffected ADA, treatment-induced ADA, or treatment-boosted ADA (denominator: number of evaluable participants);
- ADA unevaluable participant = participant classified as ADA unevaluable or with missing baseline ADA sample or without postbaseline ADA samples (in case no ADA data are available at all, the participant cannot be classified).

Document: BIOSdata\argenx\Efgartigimod\HAB40220\Biostatistics\Documentation\SAP

Author: 1.0 Version Number:

> Version Date: 03 June 2024

Template No.: CS\_TP\_BS016 Revision 7 Reference: CS\_WI\_BS005

Page 45 of 54

Note: A 4-fold difference in titer values is considered significant if a 2-fold serial dilution is applied (= 2 times the dilution factor).

**Frequency tabulations** (number and percentages) will be provided with ADA negative/positive/unevaluable samples per visit.

Frequency tabulations (number and percentages) will be provided in 1 table for:

- ADA unevaluable Participants
- ADA baseline positive/negative/unevaluable samples
- Participants per ADA participant classification
- Prevalence and incidence of ADA

**Correlation tables** by ADA against efgartigimed participant classification will be provided for the following parameters:

- Mean drug concentration over time
- Mean percent change from baseline in [total IgG]
- COMPASS-31 and MaPS
- TEAEs by MedDRA SOC and PT
- Serious TEAEs by MedDRA SOC and PT
- Injection/infusion-related reactions

ADA against efgartigimod titer values will be summarized using descriptive statistics by ADA participant classification at each analysis visit.

All available data for ADA against efgartigimod will be listed, while also showing the ADA sample status and participant classification.

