## 15.4. Immunogenicity Analysis

Incidence and prevalence of antidrug antibodies (ADA) against efgartigimod will be assessed in the SAF for the FPA. ADAs to efgartigimod is measured at the time points specified in the schedule of activities of protocol, primarily at baseline, week 1, 4, 12, 24, 48 and SFV.

Immunogenicity samples are analyzed in a 3-tiered approach:

- All samples are evaluated in the ADA screening assay and are scored ADA screening positive (tier 1) or negative.
- If a sample is scored positive in the ADA screening assay, it is further evaluated in the confirmatory assay (tier 2) and is scored confirmed positive (positive immuno-depletion) or confirmed negative

Document: BIOSdata\argenx\Efgartigimod\HAB40220\Biostatistics\Documentation\SAP

Author: Version Number: 1.0

Version Date: 03 June 2024

Template No.: CS\_TP\_BS016 Revision 7 Reference: CS\_WI\_BS005

Page 42 of 54

(negative immuno-depletion).

• If a sample is scored as confirmed positive, the samples are further characterized in the ADA titration assay (to determine titer).

If available, a titer result will be reported for the ADA confirmed positive samples. However, a titer result is not always available:

- If the ADA confirmed positive sample could not be run in the titration assay (e.g., due to insufficient sample volume/quality to perform the titer analysis), the result will be described as "positive immunodepletion", and the sample should be considered ADA positive.
- If a sample is negative in the titration assay, it will be reported as "negative titer", but it should be considered ADA positive because it was confirmed positive in the second tier.
- If a sample could not be analyzed or reported as "positive screen", the ADA sample status is ADA unevaluable.

An overview of this 3-tiered approach and all possible ADA sample results that will be reported by the laboratory is given below. From these reported ADA sample results, a final ADA sample status must be derived during the statistical analysis, as presented in the final column ("Final ADA Outcome"):

Document: BIOSdata\argenx\Efgartigimod\HAB40220\Biostatistics\Documentation\SAP

[figure not shown]
Author: Version Number: 1.0

Version Date: 03 June 2024

Template No.: CS TP BS016 Revision 7 Reference: CS WI BS005

Page 43 of 54

Figure 1: ADA Sample Status

<sup>a "Positive titer" is reported if it was not possible to retrieve a numerical value.

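### ADA prevalence in SAP 15.4 leaves out participants who are positive both at baseline and after baseline when a decisive titre is missing, although prevalence does not need the titre

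*SAP*

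**What the plan says.** Incidence and prevalence of ADA over the 48-week treatment period is a secondary endpoint (protocol Section 3, Table 3; SAP Section 2). SAP 15.4 sets three layers of rules.

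- **Sample level.** A tier-2 confirmed-positive sample that could not be run in the titration assay is reported without a titre, "and the sample should be considered ADA positive". The SAP acknowledges that a titre cannot always be obtained.
- **Participant level (Table E).** Baseline status is crossed with the highest post-baseline status. The ranking, from low to high, is: unevaluable, negative, positive with missing titre, positive with negative titre, and finally "ADA positive with titer ≥1 (numerical value selecting the sample with highest titer".
- **Endpoint level.** Prevalence is "ADA prevalence = percentage of participants with treatment-unaffected ADA, treatment-induced ADA, or treatment-boosted ADA (denominator: number of evaluable participants". The denominator is fixed by "ADA evaluable participant = participant classified in any of following categories: ADA negative, treatment-unaffected ADA, treatment-induced ADA, or treatment-boosted ADA". The excluded group is "ADA unevaluable participant = participant classified as ADA unevaluable or with missing baseline ADA sample or without postbaseline ADA samples".

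Incidence uses the same denominator and counts only treatment-induced and treatment-boosted participants.

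**The concern.** Table E is built to answer an incidence question: did ADA appear or rise on treatment? For a participant already positive at baseline, that needs two titres to compare. Prevalence asks only whether ADA was present, yet it inherits the same evaluability rule. A participant with confirmed ADA at both times can therefore be left out of a figure meant to count participants with ADA.

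The entry condition is baseline positivity. Baseline here is the last non-missing parent-study value (SAP 6.2). The parent study randomised 2:1 to efgartigimod and dosed to week 23 (protocol Section 2), so many participants reach this baseline already exposed. Positivity at baseline is thus more plausible than in a first-exposure trial, although the documents do not quantify it. Protocol 9.3.1 also calls for summaries by parent treatment, so any loss could fall unevenly between those two groups.

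**Working it through.** The documents state no ADA prevalence to reproduce. The check is to read Table E cell by cell against the prevalence definition, and then to work out the direction and possible size of the effect.

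**Step 1. Table E for known positives with results at both times**

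| Baseline | Highest post-baseline status | Table E class | In prevalence? |
|---|---|---|---|
| Negative | Positive, titre missing | Treatment-induced | Yes |
| Negative | Positive, titre available | Treatment-induced | Yes |
| Positive, titre missing | Negative | Treatment-unaffected | Yes |
| Positive, titre missing | Positive, titre missing | Unevaluable | **No** |
| Positive, titre missing | Positive, titre available | Unevaluable | **No** |
| Positive, titre available | Negative | Treatment-unaffected | Yes |
| Positive, titre available | Positive, titre missing | Unevaluable | **No** |
| Positive, titre available | Positive, below 4 times baseline | Treatment-unaffected | Yes |
| Positive, titre available | Positive, at least 4 times baseline | Treatment-boosted | Yes |

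Here *titre available* includes a negative titre, which the SAP sets to 1.

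**Step 2. Is the titre needed?** In each of the three excluded cells the participant must be either treatment-unaffected or treatment-boosted. Both belong to the prevalence numerator, so the unknown titre cannot change prevalence status. It can change incidence status, because only boosted counts there.

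**Step 3. Internal logic.** Compare rows 3 and 4. Positive without a titre and then negative is counted as prevalent. Positive without a titre and then positive again is removed. The participant with more evidence of ADA is the one dropped.

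**Step 4. When it is triggered.** With a missing baseline titre, any post-baseline positive triggers it. With a known baseline titre, the ranking means one numerical or negative titre at any post-baseline visit displaces the missing one. The drop then needs every post-baseline positive sample to lack a titre. Samples are planned at weeks 1, 4, 12, 24, 48 and the safety follow-up visit.

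**Step 5. Direction.** Let N be the participants who would be evaluable if the three cells were included, u those in the three cells, and k the positives that the SAP counts.

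- SAP prevalence: k/(N − u)
- Prevalence with the cells included: (k + u)/N
- Difference: (k + u)/N − k/(N − u) = u(N − u − k) / [N(N − u)]

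For u > 0 this is positive whenever k < N − u. It is zero only when every evaluable participant is already positive. The error can go only downward.

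**Step 6. Illustrative size.** N = 38 is the expected enrolment (SAP 3.2). The values of k and u are assumptions, and everyone else is taken as evaluable.

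- 5 truly prevalent, none in the cells: 5/38 = 13.2%
- 5 truly prevalent, u = 1: 4/37 = 10.8%, which is 2.3 points low
- 5 truly prevalent, u = 2: 3/36 = 8.3%, which is 4.8 points low

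Over a grid of k from 2 to 20 and u from 1 to 4, the shortfall runs from 1.2 points (k = 20, u = 1: 54.1% against 55.3%) to 9.9 points (k = 2, u = 4: 5.9% against 15.8%). With u = 0 it is nil.

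**The case against.** Several points on the other side are sound.

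- **The trigger is narrow.** A reader might infer that any positive participant who lacks a titre is lost. Table E does not support that. Baseline-negative participants with an untitrated post-baseline positive are treatment-induced and counted. Where the baseline titre is known, one post-baseline titre is enough to keep the participant in. This stands.
- **The sample rule is not contradicted.** A reader might infer that Table E conflicts with the statement that untitrated confirmed positives are positive. That statement concerns samples, Table E concerns participants, and the per-visit sample tables respect it. This stands. The fault is that an incidence classification is reused for prevalence.
- **The loss can be traced.** SAP 15.4 plans counts of unevaluable participants, baseline sample status, every participant class and full listings. A careful reader could rebuild the figure. This stands, but the reported endpoint would remain uncorrected.
- **The shift is small against sampling error.** The exact 95% interval for 5/38 is 4.4% to 28.1%, the endpoint is descriptive, and no hypothesis is tested. This limits the importance. It does not justify an avoidable one-directional error.
- **A shared denominator is tidy.** With one evaluable set, the four classes add up and incidence nests within prevalence. That is a reasonable preference, but not a reason to remove known positives.

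**Conclusion.** The concern holds in a limited form. Three Table E cells remove participants who are ADA positive at both times and whose prevalence status is certain. The prevalence rule understates the endpoint whenever one of these cells is occupied and at least one evaluable participant is negative.

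A reader might go further and conclude that prevalence will be understated in this study. The documents do not support that: they give neither the missing-titre rate nor baseline ADA positivity, and the effect is nil if no decisive titre is missing. The 10.8% and 8.3% figures rest on an assumed 5 of 38 prevalent, with one or two of them in the affected cells and all other participants evaluable.

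Table E also excludes some participants with a positive result at one time and an unevaluable result at the other. That follows from the SAP's separate requirement for usable results at both times, and it is not part of this point. Treating the three cells as unevaluable for incidence is correct. Overall this is a minor definitional fault in a secondary endpoint.

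**What to change.** Add one sentence to the definitions under Table E in SAP 15.4. For prevalence only, participants positive at baseline and post-baseline are counted in both numerator and denominator even if Table E classes them as unevaluable because of a missing titre. The three cells are missing/missing, missing/available and available/missing. Keep them unevaluable for incidence, leave all other evaluability rules unchanged, and footnote the two denominators in the table.

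A wider denominator, such as everyone with at least one evaluable sample, is not advised. It would admit participants with no baseline or no post-baseline sample, whom the SAP deliberately treats as unevaluable. Someone with a single negative baseline sample would then count as non-prevalent.

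The cost is one sentence, one footnote and a second denominator. Incidence and prevalence would no longer share a denominator. No new data are needed, and because SAP 15.4 plans the ADA analysis for the final analysis only, the interim analysis is not affected.

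### The safety tables by ADA class use one whole-study label and ignore event date, so they cannot show whether ADA came before a reaction

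*SAP*

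**What the plan says.** SAP 15.4 introduces Table E as showing "how the ADA participant classification will be derived, starting from the participant baseline ADA sample status". Baseline status is crossed with one postbaseline summary, defined in the table note as "Highest sample status, with order (from low to high): ADA unevaluable, ADA negative, ADA positive", with the positive categories ranked above that by titer. Each participant gets one class. A participant negative at baseline with any positive sample later is treatment-induced. One who starts positive and reaches at least four times the baseline titer is treatment-boosted. These two classes make up the incidence measure: "ADA incidence = percentage of participants with treatment-induced or treatment-boosted ADA".

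The same section then plans correlation tables "by ADA against efgartigimed participant classification will be provided for the following parameters". The list includes "TEAEs by MedDRA SOC and PT", "Serious TEAEs by MedDRA SOC and PT" and "Injection/infusion-related reactions".

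SAP 14.1 counts an event as treatment-emergent from the first dose in this study to 60 days after the last dose. It ties infusion-related reactions to a 48-hour window after an infusion. Neither definition refers to ADA timing, and neither document splits events or person-time at ADA onset.

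**The concern.** The label depends on every postbaseline sample, yet it is applied to events from the first dose onward. Someone negative at weeks 1, 4, 12 and 24 and positive at week 48 has a reaction at week 2 shown under treatment-induced ADA, although three later samples, at weeks 4, 12 and 24, were negative.

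The Protocol's risk table (2.3.1) and its section on infusion reactions (8.4.7.1) name immune responses to the protein as a possible source of hypersensitivity reactions. Readers will therefore look to these tables for a link between ADA and reactions. The first question is which came first, and the tables as planned do not answer it.

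**Working it through.** The plan gives no figure on this point to reproduce. The check is how much of a participant's exposure must, or may, precede ADA onset.

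**Inputs**
- ADA samples: baseline, weeks 1, 4, 12, 24, 48 and the safety follow-up visit (SFV) (SAP 15.4). Those on dosing days are predose (Protocol Table 1).
- Q2W infusions: weeks 0, 1, 2, 3, then every second week from 4 to 46 (Protocol Table 1), so 4 + 22 = 26.
- Treatment-emergent window: day 1 to final dose + 60. With the final Q2W dose on day 323, 323 + 60 = 383 days.
- SFV: day 323 + 56 = 379.
- Assumed: no missed samples and no extra ones between scheduled visits.

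**Bounds.** True onset lies after the last negative sample and no later than the first positive one. The lower bound counts infusions, or days, before the last negative sample. The upper bound counts those before the first positive sample. Share of window = (sample day − 1)/383.

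| First positive | Last negative | Infusions before onset, of 26 | Share of window before onset |
|---|---|---|---|
| Week 12 (day 85) | Week 4 (day 29) | 4 to 8 (15–31%) | 28/383 to 84/383 = 7–22% |
| Week 24 (day 169) | Week 12 (day 85) | 8 to 14 (31–54%) | 84/383 to 168/383 = 22–44% |
| Week 48 (day 337) | Week 24 (day 169) | 14 to 26 (54–100%) | 168/383 to 336/383 = 44–88% |
| SFV (day 379) | Week 48 (day 337) | 26 (100%) | 336/383 to 378/383 = 88–99% |

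For participants who return to QW dosing, the window is 390 days. The shares at days 29, 85, 169 and 337 become 7.2%, 21.5%, 43.1% and 86.2%; infusion counts depend on the switch date.

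**Dilution.** Suppose the event rate is constant and is multiplied by R from onset. If a share p of the window precedes onset, the whole-study rate ratio against ADA-negative participants is p + (1 − p)R. With an assumed R = 2 this is 2 − p:
- first positive at week 12: 1.93 down to 1.78
- week 24: 1.78 down to 1.56
- week 48: 1.56 down to 1.12.

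**Association when ADA have no effect.** A simulation of 500,000 participants per scenario assumed 10–30% ADA onset by week 48, 0.5 events per person-year and 0–40% discontinuation by week 46. None of these inputs is in the documents. With no ADA effect:
- With complete follow-up, the ratio of participants with at least one event, ADA-positive to ADA-negative, was 1.00.
- With 20–40% discontinuation it rose to 1.05–1.13, because longer follow-up gives more chance of both a positive sample and an event.
- The ratio of event rates per person-time stayed at 0.99–1.00.

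The upward bias therefore affects participant percentages, not rates. This matters because SAP 14.1.1 gives SOC/PT tables as participant counts, percentages and event counts; rates per 100 person-years are specified for the overview table.

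The same simulation showed a true ratio of 2.0 as 1.36–1.40 in whole-study rates. It started the effect at the first positive sample, so that result is the late-onset case. For the same reason, its recovery of about 2.0 when time is split at that sample is built in and does not show that such a split is right.

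**The case against.** The tables are descriptive. Protocol 9.1 tests no hypothesis, 9.3.1 rules out inferential use, and the immunogenicity endpoint is incidence and prevalence of ADA. SAP 15.4 does not say what the correlation tables are for. All AEs and all ADA results are listed, and SAP 6.1 puts the study day in every listing with an event or assessment date. With about 38 participants, time order can be checked case by case. This stands, and it limits the harm. However, the SAP does not require anyone to set event onset against ADA onset. The output templates, which might do so, are not among the documents.

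A reader might infer that every infusion reaction in someone first positive at week 48 is wrongly attributed to ADA. The documents do not support that. The previous sample is 24 weeks earlier, so only 14 of the 26 infusions are certain to precede onset. The full 26 is certain only for a first positive at the SFV. The tables also describe groups and do not assign cause.

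A reader might also infer that the grouping produces a false safety signal. With equal follow-up and no ADA effect, it does not.

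Finally, moving all time before the first positive sample into ADA-negative time looks like the natural repair. It would misplace events that fall between true onset and detection, a gap of up to 24 weeks.

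**Conclusion.** The point holds as a limit on interpretation. The safety tables in SAP 15.4 place events that precede a documented negative sample under treatment-induced ADA, and events before the titer rise under treatment-boosted ADA. The effect is dilution of any true association, possible upward bias in participant percentages when follow-up differs, and loss of time order.

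The size depends on when the first positive sample falls. It is modest at week 12 and large at week 48 or the SFV. The infusion ranges rest on the Q2W schedule with no missed samples; the rate ratios rest on assumed effects and event rates. No error rate or primary result is affected. It is worth correcting because the correction is cheap and restores the one piece of information that the tables lack.

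**What to change.** Keep the planned tables. For treatment-induced and treatment-boosted participants, add TEAEs, serious TEAEs and infusion-related reactions by onset in three periods:

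1. Up to the last negative sample before the first positive one. For boosted participants, use the last sample with titer below four times baseline before the rise.
2. Between that sample and the first positive (or first at least 4x) sample.
3. On or after the first positive (or first at least 4x) sample.

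Give event counts and treatment-emergent person-time for each period. Do not pool the second period with ADA-negative time, because onset falls somewhere within it. A missed or unevaluable sample widens the second period.

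The cost is SAP wording, a dating rule for boosted participants and two date comparisons. AE start dates and sample dates are already collected, and SAP 14.1 already defines treatment-emergent follow-up time. SAP 15.4 assesses ADA for the final analysis, so interim outputs need not change. The main drawback is small cells: at an assumed 10–30% ADA rate, 0.10 × 38 to 0.30 × 38 is about 4 to 11 people.
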